8.3.2 Disease characteristics

The following disease characteristics at baseline will be summarized by cohort for patients in the Safety set for each part of the trial (Part 1A and Part 1B).

- Time from initial cancer diagnosis to enrollment (months)
- ECOG Performance Status at baseline
- Time from most recent progression (as recorded on the cancer classification and staging eCRF page) to start of any trial treatment (BNT411, atezolizumab, carboplatin or etoposide)
- Location at initial diagnosis

Time from initial cancer diagnosis to enrollment (months) will be calculated as:

Time = date of enrollment – initial diagnosis date + 1.

In order to calculate the time from initial cancer diagnosis, the following rules will be applied for partial dates of first diagnosis:

- The first day of the month will be assumed;
- If the month is missing, January 1st will be assumed.

Time from most recent progression to start of any trial treatment to start of any trial treatment will be calculated as:

Time = date of first dose of BNT411 - date of most recent progression + 1.

A listing of disease characteristics will be provided.

8.3.3 Prior anti-cancer treatments

The summary of prior anti-cancer treatments will be based on the Safety set and will be presented by cohort and total for each trial part (Part 1A and Part 1B).

For prior systemic cancer therapy, the following will be summarized:

- The number of prior systemic therapies (0,1, 2, 3+)

The last prior systemic cancer therapy prior to treatment start date (the prior systemic therapy with start date closest to treatment start date) will be summarized as follows:

- Setting (adjuvant, neoadjuvant and metastatic)
- Intent (curative, palliative and unknown)
- Best response during the therapy (CR, PR, progressive disease, stable disease, unknown)
- Reason for discontinuation of last prior systemic therapy

The treatment intent and setting for prior cancer radiotherapy and treatment intent for prior cancer surgery will be summarized by cohort and total for each trial part.

Prior systemic cancer therapies will be coded using the World Health Organization Drug Dictionary (WHO DD) version B3 dated March 2023 resulting in anatomical-therapeutic-chemical (ATC) codes indicating therapeutic classification.

The number and percentage of patients taking prior systemic cancer therapies will be summarized by ATC therapeutic class (ATC level 2), ATC pharmacological class (ATC level 3), and chemical subgroup (ATC level 4) for each cohort and total for each part of the trial (Part 1A and Part 1B).

Prior cancer surgeries will be coded using the Medical Dictionary for Regulatory Activities (MedDRA[®]) coding system version 26.0 or higher and will be listed only.

A listing of prior cancer therapies (systemic cancer therapy, cancer radiotherapy, cancer surgery) will be provided.

8.3.4 Prior and Concomitant medication/Procedures/Non-drug Therapy

Prior and concomitant medications will be defined using medication start and stop dates recorded, relative to the first and last dose of trial treatment (BNT411, atezolizumab, carboplatin, etoposide) for both the trial parts (1A and 1B).

A **prior medication** will be defined as any therapy taken 28 days prior up to (but not including) the start date of trial treatment.

A concomitant medication will be defined as any medication either ongoing at the start of trial treatment in each trial part (1A and 1B) or with a start date on or after the first dose of any trial treatment up to (but not including) the last date of trial treatment (BNT411, atezolizumab, carboplatin, etoposide). See Section [8.1](#) for handling missing dates.

Medications will be coded using the World Health Organization Drug Dictionary (WHODrug) drug codes of version B3 dated March 2023. Resulting in ATC codes indicating therapeutic classification.

The number and percentage of patients who had prior and concomitant medications will be summarized by ATC therapeutic class (ATC level 2), ATC pharmacological class (ATC level 3), and chemical subgroup (ATC level 4) for each cohort and total within each trial part based on the Safety set. The summary will be presented alphabetically.

A listing of prior and concomitant medications will be provided.

Procedures and Non-drug therapies will be coded using the Medical Dictionary for Regulatory Activities (MedDRA[®]) coding system version 26.0 or higher. Procedure and non-drug therapies will be listed only.

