# 6.5 Concomitant Therapy and Procedures

Any medication or vaccine (including over-the-counter or prescription medicines, vitamins, and/or herbal supplements) or procedure that the patient is receiving or undergoing at the time of signing the Informed Consent Form, or receives or undergoes during the trial must be recorded along with, as applicable:

- reason for use
- dates of administration including start and end dates
- dosage information including dose and frequency.

The Medical Monitor should be contacted if there are any questions regarding concomitant or prior therapy.

Concomitant anti-emetics, anti-diarrheal agents, intravenous fluids, or electrolyte replacement based on clinical or laboratory assessments and blood transfusions while on treatment based on individual institutional guidelines will be allowed.

Radiotherapy should be documented in the eCRF including total dose, fractionation and location. The prohibited medications while on trial treatment are as follows:

- Other anti-cancer therapy not included under trial treatment in a given part of the trial (e.g. Part 1A, Part 1B and Part 2).
- Other prohibited concomitant medications as listed in inclusion and exclusion criteria (Section 5.1 and Section 5.2).
- No systemic anti-cancer therapies should be administered concurrently with PCI. A delay of ≤21 days in administering systemic anti-cancer therapies due to PCI is not considered a protocol deviation.
- For further guidance on prohibited and restricted medications, please refer to the IB for BNT411, and USPI or SmPCs for atezolizumab, carboplatin and etoposide.

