#### 6.5.1 Premedication

As part of its intended mode of action, BNT411 is expected to induce a discrete spectrum of cytokines. These may be associated with flu-like symptoms within the first hours after administration.

Routine premedication with analgesics or anti-pyretics such as acetaminophen/paracetamol, ibuprofen, naproxen, or aspirin at established doses and schedules can be given at the investigator's discretion and patients can be appropriately prehydrated prior to treatment.

Because of their immune-suppressive effect, premedication with corticosteroids should be minimized to the extent that is clinically feasible. The use of corticosteroids as anti-emetics or for any other purposes may be substituted with other drugs from different classes per investigator's discretion. All premedication must be reported on the concomitant medication page in the eCRF.

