#### **6.6.4.2 Infusion-Related Reactions (IRRs)**

IRR is a general risk to be considered for any new compound administered intravenously irrelevant of its MoA. IRR is typically of immediate onset after the compound's administration. We cannot exclude the risk of IRR with BNT411 due to the given limited experience with BNT411.

The following treatment guidelines are provided below for patients who experience an IRR associated with administration of BNT411 treatment.

- Grade 1- If an IRR Grade 1 occurs, the infusion does not need to be interrupted and can be continued at the investigator's discretion at half the infusion rate under close medical supervision.
- Grade 2-3- If an IRR Grade 2 or Grade 3 occurs, the infusion should be interrupted and appropriate medical management instituted. The infusion may be re-started at the investigator's discretion at half the infusion rate under close medical supervision if symptoms have resolved to Grade ≤1 within an hour.
  - Patients who have experienced prior infusion related Grade 2 or Grade 3 reactions in the trial should be premedicated. Premedication to prevent IRR in subsequent infusions may be administered at the investigator's discretion according to local guidelines but preferably includes an antihistamine (e.g., diphenhydramine 50 mg orally twice daily [po] or equivalent antihistamine), acetaminophen/paracetamol (e.g. acetaminophen 500-1000 mg po or equivalent), and if considered necessary, patients should receive corticosteroids at a suggested maximum dose of 100 mg prednisone or equivalent.
  - o If the patient has a second Grade 3 IRR despite premedication, the infusion should be stopped and the patient should be withdrawn from treatment.
- Grade 4- If anaphylaxis or Grade 4 IRR occurs, administration of BNT411 should be discontinued immediately and permanently, and appropriate medical therapy should be administered.

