8.5.2 Adverse events

This section includes the description of the analysis planned for the primary endpoints on this trial.

AEs will be coded using the most recent version of Medical Dictionary for Regulatory Activities (MedDRA®) coding system version 26.0 or higher to get a SOC and PT for each AE and graded for severity using NCI CTCAE v5.0. In case a patient has an AE with missing relationship status, the event will be assumed to be related and associated with the treatment received in the summaries (will be listed as collected in the listings). No imputation for missing NCI-CTC grades will be performed.

A treatment-emergent AE (TEAE) is defined as any AE with an onset date on or after the first administration of trial treatment (BNT411 in part1A and BNT411, atezolizumab, carboplatin, and etoposide in Part 1B) (if the AE was absent before the first administration of trial treatment) or worsened after the first administration of trial treatment (if the AE was present before the first administration of trial treatment). AEs with an onset date more than 60 days after the last administration of trial treatment will be considered as treatment-emergent only if assessed as related to trial treatment (BNT411 for Part 1A and BNT411, atezolizumab, carboplatin, and etoposide for Part 1B) by the investigator.

Treatment-emergent AEs will be summarized by cohort and trial part and total within trial part. In addition, treatment-related TEAEs will be summarized by cohort and trial treatment (BNT411, atezolizumab, carboplatin, and etoposide) within trial part.

Only TEAE data will be summarized for the Safety set for each trial part (Part 1A and Part 1B). Non-TEAEs will be listed only.

Dose-limiting toxicities

In general, a DLT for a drug or other treatment is defined as one or more AEs that prevents an increase of the dose level of that treatment (for details on dose escalation decision rules see Appendix 5).

Serious AEs (SAEs), non-serious grade ≥ 3 AEs and clinically significant abnormal laboratory values grade ≥ 3 will be collected and assessed for DLTs (for each dose level during the first cycle). Common Terminology Criteria for Adverse Events (NCI CTCAE) v.5.0 will be used to grade the intensity of AEs.

More details regarding DLTs can be found in the Section 6.6 of the CTP.

For the additional rules and considerations of MTD and RP2D other than what was already defined in Section 1.1, see Section 4.1.1.2 of the CTP.

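### Drugs newly started on or after the last dosing day are neither prior nor concomitant under SAP 8.3.4, so the medication table can under-count first-time treatment of reactions to the final infusion

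*SAP*

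**What the plan says.** SAP 8.3.4 sorts medications by their dates relative to the first and last dose of trial treatment, and names all four drugs (BNT411, atezolizumab, carboplatin, etoposide).

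- **Prior:** "any therapy taken 28 days prior up to (but not including) the start date of trial treatment".
- **Concomitant:** either already ongoing when trial treatment starts, or newly started "on or after the first dose of any trial treatment up to (but not including) the last date of trial treatment".

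No third category is defined. The section then promises a table of patients with prior and concomitant medications by ATC class, by cohort and in total within each trial part, on the Safety set. SAP 8.1 bases percentages for event-type data, with concomitant medication named as an example, on all patients in the analysis set.

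Other parts of the plan use a longer period. SAP 8.5.2 requires a relationship to trial treatment only for "AEs with an onset date more than 60 days after the last administration of trial treatment"; before that limit, any new or worsened event counts as treatment-emergent. Protocol 6.5 states that whatever the patient "receives or undergoes during the trial must be recorded along with, as applicable", its reason, dates and dosage, with no stop at the last dose. The schedules of activities show medication recording as continuous, and as continuing into survival follow-up for BNT411-related events.

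**The concern.** The window for new starts closes one day too early and nothing follows it. A drug given for the first time on the day of the final infusion, or on any later day, has no category. The event it was given for is still counted as treatment-emergent.

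The gap falls at a sensitive point. On reactions to BNT411-induced cytokines, Protocol 6.5.1 says: "These may be associated with flu-like symptoms within the first hours after administration". Protocol 6.6.4.2 adds: "IRR is typically of immediate onset after the compound's administration". Treatment for such reactions will usually start on the infusion date. Protocol 6.6.4.2 and 6.6.5 make some severe reactions the end of BNT411 treatment, for example anaphylaxis, a Grade 4 infusion-related reaction, or Grade 4 cytokine release syndrome. In those cases the infusion that caused the reaction becomes the last one, and the drugs first used to treat it are the ones the rule leaves out. Premedication newly started on the last dosing day is dropped in the same way.

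**Working it through.** The plan gives no figure to reproduce, so the check applies the date rules to example patients.

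**Inputs.** F = first and L = last date of any trial treatment, S = start date of a drug. Prior and concomitant rules are from SAP 8.3.4, the 60-day adverse event limit is from SAP 8.5.2, and BNT411 dosing in Part 1A (Days 1, 8 and 15 of 21-day cycles for four cycles) is from Protocol 6.1.1.

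**Rules.** New start is concomitant if F ≤ S < L. The main treatment-emergent window is F to L + 60. With F = Day 1, the new-start window has L − 1 days and the adverse event window has L + 60 days. The difference is (L + 60) − (L − 1) = 61 days: the last dosing day plus 60.

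| Part 1A patient | L | New-start window (L − 1) | Adverse event window (L + 60) | Uncovered |
|---|---|---|---|---|
| One infusion | 1 | 0 days | 61 days | 61 days |
| Cycle 1 only | 15 | 14 days | 75 days | 61 days |
| Four full cycles | 3 × 21 + 15 = 78 | 77 days | 138 days | 61 days |

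**Classification.**
- S = L: fails S < L, and is not before F. Neither prior nor concomitant.
- S = L + 1: the same.
- S = L − 1: concomitant, where there is more than one dosing date.
- Ongoing from before F: always concomitant.

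**Missing-date rules.** SAP 8.1 imputes partial medication dates. It does not change the window for complete dates, so it does not close the gap.

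**Part 1B.** L is the latest date across four drugs. In chemotherapy cycles BNT411 is given on Day 2 and etoposide on Day 3. A drug started on Day 2 for a BNT411 reaction is captured if etoposide follows on Day 3 (2 < 3). If the last trial drug of any kind is BNT411 on Day 8 or Day 15, then S = L and the drug is lost.

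**Effect on a percentage.** A patient whose only use of an ATC class began on or after L counts as a non-user, with N unchanged. The cohort figure for that class then drops by 1/N: 100 percentage points in a single-patient cohort, 33 with three patients, 17 with six, and 7 with 14 (the backfill limit in Protocol 4.1.1.1). These are shifts per affected patient. The documents do not allow the number of affected patients to be forecast.

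**Trial fixes.** Changing the rule to S ≤ L recovers S = L but not S = L + 1. Extending it to S ≤ L + 60 recovers both.

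**The case against.** The records are not lost. Medications are collected throughout, SAP 8.1 promises that all collected data will be listed, and Protocol 10.3.3 has the investigator record drug treatment started for an adverse event. With cohorts this small, a reader can find the drug in a listing. That stands, and it limits the problem to the classification and the ATC table.

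The table counts patients, so anyone given the same class at an earlier infusion is already counted. Totals for antipyretics may barely move. That also stands; the exposure is first-time use.

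An on-treatment definition of concomitant is legitimate, and nothing in the documents requires it to match the adverse event window. That stands as an argument about which fix to choose. It does not defend leaving out the last treatment day itself, or leaving later drugs without any category.

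Three stronger readings are tempting and are not supported:

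- **Most reaction treatment is missed.** A reader might take 14/75 = 19% coverage for a Cycle 1-only patient as the size of the under-count. It is a ratio of calendar days. Reaction treatment clusters around infusions, and the same ratio for four cycles is 77/138 = 56%. Neither measures missed drugs or patients.
- **The primary safety objective is affected.** No primary endpoint in SAP 3.1 uses the medication flag, and the medication table is not in the list of safety summaries in SAP 8.5.
- **Every patient who stops for toxicity is affected.** Several stopping rules in Protocol 6.6.3 and 6.6.4.2 need a repeat event or more than two dose reductions. Drugs started at the earlier occurrences are counted.

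**Conclusion.** The rule is wrong as written, not merely short of detail: it yields a definite and incorrect answer for a drug first given on the last treatment day. The conclusion assumes that the definition is programmed literally and that medication start dates are complete.

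The likely direction is under-counting of drugs first used to treat a reaction to the final infusion. Part 1A is fully exposed; Part 1B only where no trial drug of any kind is given later. The size in the real data depends on how many patients first needed such a drug at or after their last dose, which the documents do not give. DLT counts, adverse event summaries, listings and the escalation, MTD and RP2D rules do not change. This should be corrected, but no trial conclusion depends on it.

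**What to change.** In SAP 8.3.4, include the last dosing date in the concomitant window and give later drugs a category. Either form would do:

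1. Concomitant means ongoing at first dose, or started from the first dose through 60 days after the last dose of any trial treatment. This aligns with the main treatment-emergent window; events beyond 60 days that count because they are related would still lie outside it.
2. Concomitant runs through the last dosing date inclusive, and a separately summarised post-treatment category covers drugs started from the next day through day 60.

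Including the last date alone is not enough, because a drug started the next day would remain unclassified. Under either form, keep new anti-cancer therapy in its own listing (SAP 8.6.3).

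The cost is one SAP sentence and one derivation change, plus one further summary under the second form. No new data are needed.

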8.3.5 Medical history

Medical history data will be coded using Medical Dictionary for Regulatory Activities (MedDRA[®]) version 26.0 or higher. The number and percentage of patients with each medical history will be summarized by System Organ Class (SOC) and Preferred Term (PT) for each cohort and total within each trial part based on the Safety set.

A listing of medical history data will be provided.

8.4 Efficacy analyses

Owing to the heterogeneity of cancer types and limited number of patients in Part 1A and B, no efficacy analysis will be done in Part 1.

8.4.1 Primary analysis

Not applicable for this trial as there is no primary efficacy endpoint defined for this trial. The primary endpoint is a safety endpoint, this endpoint is described in Section [8.5.2](#).

8.4.2 Supplementary analyses

Not applicable.

8.4.3 Secondary analyses

Not applicable.

8.4.4 Exploratory analyses

Not applicable.

8.5 Safety analyses

Safety data that will be summarized includes treatment exposure, AEs, clinical safety laboratory assessments (including hematology, biochemistry, urinalysis, coagulation endocrine tests), vital signs, electrocardiogram (ECGs), ECOG PS, Eye examinations, PD and biomarkers. All safety analyses will be based on the Safety set and will be summarized by cohort and trial part and if appropriate, by cohort and treatment, for example for summary of treatment-related AEs. For all the summaries patients will be assigned to the treatments according to the actual treatment they have received ("as treated"). The actual treatment will be derived as following:

- If a patient received at least once the planned dose during Cycle 1, then this patient will have the actual treatment assigned to the planned treatment.
- Otherwise, the actual treatment will be considered as the dose received in Cycle 1 day 1.

All safety data will be listed.

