# 6.1.1 BNT411

In Part 1A, BNT411 will be administered using a 100 mL intravenous infusion on Days 1, 8 and 15 of each 3-week treatment cycle (21 days) of the first 4 cycles after all required procedures and assessments have been completed. In the following cycles thereafter, BNT411 will be administered every 3 weeks on Day 1 of each 3-week treatment cycle (21 days) after all required procedures and assessments have been completed.

In Part 1B, BNT411 will be administered using a 100 mL intravenous infusion on Days 2, 8 and 15 of each 3-week treatment cycle (21 days) of the first 4 cycles after all required procedures and assessments have been completed. In the following cycles thereafter, BNT411 will be administered every 3 weeks on Day 2 of each 3-week treatment cycle (21 days) after all required procedures and assessments have been completed.

In both Part 1A and Part 1B, patients will be administered BNT411 according to dose levels outlined in Table 4-2. BNT411 will be administered as a body weight-based dosing. A cap on dosing for patients weighing 120 kg and more will be implemented in the proposed clinical trial.

In Part 1B, for combination with atezolizumab and chemotherapy, the administration will be in the following order:

Day 1: Atezolizumab → Carboplatin → Etoposide

Day 2: **BNT411** → Etoposide

Day 3: Etoposide

For each dosing of BNT411 in Cycle 1, patients will remain in the treatment center and be closely monitored for immediate AEs for at least 6 hours. Hospitalization is required for the first 24 hours after the first BNT411 administration in Cycle 1 for clinical observation and PK sampling. Prolongation of the hospitalization beyond 24 hours may be performed at the investigator's discretion if deemed necessary based on potential risks related to the trial treatment and clinical status of the patient. For each subsequent dose of BNT411 in all cycles, patients will be monitored for at least 6 hours.

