	Route of administration: 100 mL intravenous infusion.	
Route of administration: 100 mL intravenous infusion.
 
For the purpose of this trial, in the USA and UK, atezolizumab, carboplatin and etoposide are considered as non-investigational medicinal products (NIMPs). However, the individual drugs are considered as IMPs in Spain and Germany at the request of the competent authorities due to their use in combination with BNT411.
 
Name: Atezolizumab Dose: recommended dosage is 1200 mg Schedule: Every 3 weeks Route of administration: IV infusion.
 
Name: Carboplatin Dose: commercially available formulation and at the label-recommended doses Schedule: every 3 weeks until cycle 4 Route of administration: IV infusion.
 
Name: Etoposide: Dose: commercially available formulation and at the label-recommended doses (100 mg/m²)
	Route of administration: intravenous infusion.

	Part 1A	Part 1B	Part 2
		
Schedule: On Day 1 of each cycle, administered over 60 minutes following carboplatin administration. On Day 2 and Day 3 of each cycle, administered intravenously over 60 minutes.
 
Route of administration: IV infusion.
 
For combination with atezolizumab and chemotherapy, the administration will be in the following order:
 
Day 1: Atezolizumab > Carboplatin > Etoposide
 
Day 2: BNT411 > Etoposide
 
Day 3: Etoposide
	
Planned number of patients	
The number of patients for Part 1A is driven by the 3+3 trial designBetween 6 to 60 DLT-evaluable patients are planned to be enrolled in Part 1A.	
The number of patients for Parts 1B is driven by the 3+3 trial designBetween 6 to 30 DLT-evaluable patients are planned to be enrolled in Part 1B.	
This will be implemented through a CTP amendment.
Randomization and blinding	This is a non-randomized, open-label trial		The expansion cohort may be a single-arm cohort or a randomized cohort. This will be documented in a CTP amendment.

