7 ANALYSIS SETS AND SUBGROUPS

7.1 Analysis sets

Enrolled Set

Enrolled set will have the patients with a valid date of informed consent.

Safety Set

The Safety set is defined as all patients who received BNT411 (i.e., at least one dose of BNT411).

DLT Evaluation Set

The DLT evaluation set includes all patients from the Safety set who either have completed the DLT evaluation period (i.e., have been observed for minimum 21 days following the first dose) and meet the minimum exposure criterion (i.e., when the relative dose intensity [RDI] of BNT411 in Cycle 1 is 100%) or have experienced a DLT during the DLT evaluation period (Cycle 1).

Patients who do not experience any DLT during the DLT evaluation period are considered to be evaluable if they have been observed for minimum 21 days following the first dose and are considered to have sufficient safety data to conclude that a DLT did not occur.

Patients who are excluded from the DLT evaluation set will be replaced.

Pharmacokinetic (PK) Full Set

The PK Full set will consist of all patients who receive at least one dose of BNT411 and have at least one quantifiable post-dose PK sample.

Pharmacokinetic (PK) Evaluable Set

The PK Evaluable set will consist of all patients in the PK Full Set with a sufficient number of quantifiable PK samples to reliably estimate one or more PK parameters.

Pharmacodynamic (PD) Set

The PD set is defined as all patients who received IMP (i.e., at least one dose of BNT411) and have at least one valid post-dose PD assessment.

The DLT evaluation set will be used for the evaluation of DLTs in order to assess the MTD and the RP2D. The Safety set will be used for all other safety analyses. The PK Full Set, PK Evaluable Set and PD analysis set will be used for the PK and PD summaries, respectively.

Most patient data listings will be based on the Safety set. The Enrolled set will be used to summarize the patient disposition summary and some patient data listings.

For the screened patients, the summary is not by cohort, the number and percentage of patients having failed screening (reported as screen failure in the electronic Case Report Form [eCRF]) will be presented along with a summary of the primary reason for screening failure.

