Change from baseline: Unless and otherwise specified, will be calculated as follows:

Change from baseline = post-baseline assessment value – baseline assessment value.

If either the baseline or post-baseline assessment value is missing, the change from baseline is set to missing as well.

For the derivations of PK and PD data, see Section [8.6.1](#) and [8.6.2](#).

Duration (Other than “Trial Treatment Duration” defined in Section [8.5.1](#)) will be calculated as follows:

- Duration = last observation date – first observation date + 1.

For conversion of days to months or years the following rules will be applied:

- 1 month = 30.4375 days
- 1 year = 365.25 days

Trial Day and Treatment Day will be calculated for each trial part (1A and 1B) as follows:

- Trial day:
 - If assessment date < treatment start date then trial day = assessment date – treatment start date
 - If assessment date >= treatment start date then trial day = assessment date – treatment start date + 1
- Treatment Day = treatment date – date of first dose of BNT411 +1

That is, trial day 1 indicates the date of treatment initiation.

For BNT411, it is Cycle 1 Day 1 of Part 1A and Cycle 1 Day 2 of Part 1B. For atezolizumab, carboplatin and etoposide it is Cycle 1 Day 1 of Part 1B.

All trial data will be presented as collected in the eCRF/visit assigned in external data. No windowing of data for the purposes of assigning to a visit will occur.

Unscheduled assessments will be listed only and not included in summaries/analysis.

Handling missing data:

For the purposes of assigning treatment-emergent flag for adverse events (AEs), partial or missing AE dates will be handled as follows (trial treatment date is the earliest date of BNT411 in Part 1A and earliest date of atezolizumab, BNT411, carboplatin and etoposide in Part 1B).

- If the day of the month is missing, the onset day will be set to the first day of the month unless it is the same month and year as trial treatment. In this case, in order to conservatively report the event as treatment-emergent, the onset date will be assumed to be the first date of trial treatment.

- If the onset day and month are both missing, the day and month will be assumed to be January 1, unless the event occurred in the same year as the trial treatment. In this case, the event onset will be coded to the day and month of treatment in order to conservatively report the event as treatment-emergent.

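### The as-treated fallback in SAP 8.5 returns no BNT411 dose level in Part 1B, and in Part 1A a partial dose that fits a lower cohort or none, for patients with no full planned dose in Cycle 1

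*SAP*

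**What the plan says.** SAP 8.5 sets the grouping rule for safety reporting: "For all the summaries patients will be assigned to the treatments according to the actual treatment they have received". The rule has two branches. The first keeps the patient under the planned treatment: "If a patient received at least once the planned dose during Cycle 1". The second covers everyone else: "the actual treatment will be considered as the dose received in Cycle 1 day 1".

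The day on which BNT411 starts differs by part. SAP 8.1, on the start of treatment, says: "For BNT411, it is Cycle 1 Day 1 of Part 1A and Cycle 1 Day 2 of Part 1B". Protocol 6.1.1 agrees: "In Part 1B, BNT411 will be administered using a 100 mL intravenous infusion on Days 2, 8 and 15". SAP 3.2 gives the Part 1B sequence for the first day without BNT411: "Day 1: Atezolizumab > Carboplatin > Etoposide".

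The Safety set (SAP 7.1) needs only one dose of BNT411 and does not require that the dose was complete. SAP 8.5 gives no tolerance around the planned dose and does not say how a partial dose maps to a reporting cohort.

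**The concern.** The fallback is tied to a calendar day that is right for Part 1A and wrong for Part 1B. In Part 1B, a patient whose only BNT411 exposure is a partial infusion on Day 2 is in the Safety set, but the rule looks at Day 1 and finds no BNT411. The PK section (SAP 8.6.1) repeatedly adds the Part 1B day next to Cycle 1 Day 1. The as-treated rule does not, which looks like an oversight.

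In Part 1A the day is right, but the amount received is a poor marker of the dose level under test. A patient stopped partway through the first infusion, who never gets a full dose in Cycle 1, is labelled by the fraction infused. These patients are not a random subset. Under Protocol 6.6.4.2, anaphylaxis or a Grade 4 infusion reaction ends BNT411 permanently. Under Protocol 6.6, a patient with a DLT should stop at once unless the sponsor allows otherwise. So the fallback mainly reaches patients who reacted badly at the start. Their events could be shown under a lower dose, or under none, in the final by-cohort safety tables.

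**Working it through.** The plan gives no figure on this point and tests no hypothesis (SAP 4). The check is to apply the rule literally.

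**Who reaches the fallback.** Cycle 1 has three BNT411 infusions: Days 1, 8 and 15 in Part 1A, and Days 2, 8 and 15 in Part 1B. Take a partial first infusion and let each later one be full, partial or not given: 3 × 3 = 9 patterns. Patterns with no full dose on either later day: 2 × 2 = 4. The other 9 − 4 = 5 contain a full dose and stay with the planned treatment. These are counts of patterns, not probabilities. A first infusion that is interrupted, restarted and completed delivers the planned dose and never reaches the fallback.

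**Part 1B.** All 4 fallback patterns return no BNT411 dose. Both Part 1B combination cohorts in SAP Table 4 are defined by a BNT411 level (1.2 or 2.4 µg/kg), so neither can be assigned.

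**Part 1A.** All 4 fallback patterns return the partial first dose. Taking exactly half as an assumption:

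| Planned (µg/kg) | Half | Table 4 cohort? |
|---|---|---|
| 0.05 | 0.025 | none |
| 0.15 | 0.075 | none |
| 0.45 | 0.225 | none |
| 1.2 | 0.6 | none |
| 2.4 | 1.2 | lower cohort |
| 4.8 | 2.4 | lower cohort |
| 6.0 | 3.0 | none |
| 7.2 | 3.6 | none |
| 9.6 | 4.8 | lower cohort |

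Half doses match a lower cohort at three of nine levels. Most other partial amounts match no cohort.

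**From treatment to cohort.** SAP 8.5 assigns patients to treatments and does not say that cohort membership is re-derived. Table 4 (SAP 10.3) supports reading the two as one. It is presented as a table of treatment descriptors, gives each dose-level cohort its own treatment code, and says the code will be used in the statistical procedures.

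**Effect on a crude rate.** The moved patient leaves both numerator and denominator. The cohort sizes are illustrative; 14 is the backfilling limit in Protocol 4.1.1.1.

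| Before | After | Change (points) |
|---|---|---|
| 1/3 = 33.3% | 0/2 = 0% | −33.3 |
| 1/6 = 16.7% | 0/5 = 0% | −16.7 |
| 2/6 = 33.3% | 1/5 = 20.0% | −13.3 |
| 1/14 = 7.1% | 0/13 = 0% | −7.1 |
| 2/14 = 14.3% | 1/13 = 7.7% | −6.6 |

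In a single-patient cohort, the cohort would simply be empty.

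**The case against.** The strongest reply is that the first branch already protects most patients. Under Protocol 6.6.4.2 a Grade 1 reaction need not interrupt the infusion, and a Grade 2 or 3 reaction allows a restart once symptoms settle within an hour. A full dose on Day 8 or 15 also keeps the patient in place. This stands. A reader might infer that any interrupted first infusion moves the patient out of the cohort; the documents do not support that.

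Second, SAP 8.5 distinguishes summaries by cohort from summaries by cohort and treatment, so the rule might govern only the latter. This stands in part: the link to cohort is a well-supported reading of Table 4, not a stated rule.

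Third, a reader might infer that the rule could make a dose look safer when escalation is decided. Nothing in the documents says so. Under Protocol 4.1.1.1 the SRC reviews each cohort after its DLT period, and no text links that review to this SAP derivation. All safety data are listed (SAP 8.5), treatment administration is listed by patient (SAP 8.5.1), and the DLT listing carries Cycle 1 exposure (SAP 8.5.2). A displaced patient would be visible there.

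Fourth, a reader might take 17 to 33 points as the general size. That range is not general: 2/6 to 1/5 is 13 points, and a cohort of 14 moves by about 7.

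None of this answers the Part 1B gap, or the lack of any mapping for a partial dose.

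**Conclusion.** Wrong as written, and minor. For Part 1B the finding needs no assumption beyond a patient with BNT411 exposure but no full planned dose in Cycle 1: the rule then returns no BNT411 level. For Part 1A it needs a first infusion not completed and no full dose later in Cycle 1. The value returned is then a partial dose that matches a lower cohort or none.

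The claim that events could leave the dose level that caused them further assumes that Table 4 cohorts are the treatment groups in the tables. On that reading the displacement runs mainly one way, because the patients affected are mainly those who stopped for a severe reaction or DLT. The case is expected to be rare, and the documents give no figure for how often it would occur. The consequence is limited to final descriptive safety tables. It does not extend to escalation decisions on anything the documents say.

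**What to change.** Replace the second branch in SAP 8.5 with:

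> Otherwise, the actual treatment is the BNT411 dose level prepared for and started at the first BNT411 infusion (Cycle 1 Day 1 in Part 1A, Cycle 1 Day 2 in Part 1B), regardless of whether that infusion was completed.

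This is a single criterion. An interrupted infusion of the assigned level stays in its planned cohort, and a patient reaching this branch is reassigned only if a different dose level was prepared. A true dosing error at the first infusion is therefore still captured.

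Correcting the day alone would not be enough. In the Part 1B 2.4 µg/kg cohort, a half dose on Day 2 would then return 2.4 / 2 = 1.2 µg/kg and place the patient in the lower cohort.

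The cost is one SAP sentence and the matching derivation. It changes no clinical rule.
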